1.3.2 Catheter Directed Therapy

Catheter directed therapy (CDT) of PE involves the use of mechanical thrombectomy/fragmentation, mechanical thrombectomy plus thrombolytic therapy, and catheter delivered thrombolytic therapy. The goal of catheter directed

therapy is to rapidly decrease afterload on the right ventricle while reducing clot burden. Displacement of centrally occlusive thrombus to a more peripheral distribution in pulmonary arterial branches may decrease afterload in the right ventricle, increase clot surface area for faster dissolution, but may not address overall clot burden.

Unresolved thrombi can result in persistent perfusion defects and can produce residual symptoms of reduced functional status, persistent thrombi, limitations of cardiopulmonary function.

A recent meta-analysis showed catheter directed thrombolysis was associated with lower mortality but increased risk of bleeding when compared with anticoagulation alone. It was found to be decreased however when compared with systemic thrombolytics.^{XVIII}

1.3.3 Surgical Intervention for PE

Several surgical treatment options are available for the management of PE. Historically, surgical pulmonary embolectomy has been indicated in patients who are hemodynamically unstable secondary to acute massive PE. Candidates for surgical embolectomy have failed or are not candidates for thrombolytic therapy. Surgical pulmonary embolectomy is also recommended for patients with persistent hemodynamic instability, or in patients with significant RV dysfunction that persists despite the use of fibrinolytic therapy.^{XVII}

In another study, patients with high-risk PE were assigned to either thrombolytic therapy or pulmonary surgical embolectomy. Early and late mortality, systolic pulmonary artery pressure (sPAP), right ventricular diameter (RVD), and bleeding complications were evaluated. Seventy-eight patients were treated with thrombolytic therapy and 30 patients underwent surgery. The difference between pre-intervention and third-day post-intervention in terms of RVD and sPAP was significantly greater in patients under surgical embolectomy ($P < 0.001$). There was a significant decline in RVD and sPAP in both groups during follow-up ($P < 0.001$). Mortality rate in the surgical embolectomy group was lower than the thrombolytic group, although not significantly.^{XIX} However, early surgical treatment was associated with fewer complications in comparison to thrombolytic therapy in this high-risk patient population.

[figure not shown]

Figure 6: Predictors of in-hospital mortality among patients undergoing surgical embolectomy for acute pulmonary embolism (PE) in the National Inpatient Sample. Data are shown as the odds ratio (square) and 95% confidence interval (horizontal whiskers).^{XVII}

In experienced centers, surgical embolectomy is considered to be a safe procedure with low mortality, providing improved postoperative right ventricular function and pulmonary pressure as well as improved long-term outcome. In a study of 37 consecutive cases, Edelman et al. demonstrated that elimination of a large portion of the clot burden could be lifesaving. They concluded that pulmonary embolectomy should be considered as an initial treatment strategy in patients with massive or sub-massive pulmonary embolus with a large burden of proximal clot.^{XX}

However, surgical intervention for PE remains a highly invasive procedure that relies on cardiopulmonary bypass and is limited to specialists and centers with specific training and experience.

1.3.4 The Emerging Opportunity for Embolectomy Devices to Treat PE

There has been a renewed interest in catheter-based embolectomy as the primary means of treating PE.^{XXIX} The goal of treatment for high-risk PE is to rapidly reverse hemodynamic instability given the high mortality associated with this diagnosis. For intermediate risk PE, goals are to expedite symptom resolution and avert hemodynamic decompensation. The reasons for the therapeutic shift towards devices include:

1. Although medical reperfusion strategies have lowered mortality rates in PE, survival has been slow to improve (*Figure 7*).

		After 20 years, mortality is still high in PE patients		
		1999 ICOPER ¹	2018 MGH PERT data ²	2020 PERT Consortium data ³
30-day	Mortality (High-Risk / Massive)	~51.0%	34.8%	25.9%
	Mortality (Intermediate-risk / Sub-massive)	~11.0%	8.2%	6.1%
	Major Bleeding	10.5%*	11.5%	5%

* 90-day major bleeding rate

Figure 7: From [name] University Hospital of Wales, Cardiff.

The residual risks of bleeding and death associated with intermediate risk PE and medical reperfusion strategies combined with the advent of new endovascular tools to treat PE is changing the approach to patient management in the presence of acute PE.

2. Rapid reversal of hemodynamic instability contributes to better outcomes. Patients with sub-massive PE are typically managed conservatively with anticoagulation; however, the presence of RV dysfunction has been demonstrated to predict poor outcomes, including increased mortality.^{XXI}
3. Large-bore systems (e.g., Inari Medical) have been sufficiently improved to provide better flexibility and access to the pulmonary artery anatomy.
 - a. From April 2016 to October 2017, as part of a pivotal clinical study, Inari Medical (NASDQ NARI) enrolled 106 patients at 18 sites who were treated with their FlowTrieve System, a large bore catheter system intended for the aspiration of large pulmonary artery clots. The authors reported a low complication rate (3.8%) and an average RV/LV ratio reduction of 25%.
 - b. These data were followed by a second pivotal trial conducted by Penumbra (NASDQ PEN) similar in design to Inari Medical's trial. Penumbra's Lightning-12 systems demonstrated a similar safety profile to Inari's FlowTrieve device, and a better improvement in RV/LV ratio of 43%.
4. Device intervention is associated with fewer in-hospital and ICU stays.^{XXII}

1.4 Clinical Data Driving the Use of Embolectomy Devices to Treat PE

The use of aspiration catheters to retrieve life-threatening pulmonary emboli was first described by Greenfield and colleagues in 1969.^{XXIII} Following Greenfield's experience with a large-bore but relatively stiff catheter-based device to perform aspiration embolectomy, other groups attempted similar procedures.

Aspiration thrombectomy for PE remained largely a research interest and was not routinely used to treat massive or sub-massive PE due to a high complication rate. These patients, when possible, were referred to surgery.

Both Inari Medical and Penumbra recently published data from their pivotal studies demonstrating the effectiveness of aspiration embolectomy in high-risk PE patients. These studies, in combination with ongoing studies and registries, have established a role for aspiration thrombectomy in the high-risk segment for PE. The two pivotal studies demonstrated early success by reducing the RV/LV ratio which is a surrogate marker for RH strain. Other relevant studies are summarized in *Table 2*.

Table 2: Recent studies in catheter-based pulmonary embolectomy

Study		Design			P I C O * (Patients included, Intervention, Control, and Outcome)						Results
Year	Study (Author)	Type	Sites+	Size (N)	Patients included	Age (yrs)	Female (%)	Intervention	Control	Outcome (Primary)	Based on Primary Outcome
2023	FLASH Registry ^{xxiv} (Catalin) (INARI)	Obser.	50	800	Acute intermediate- and high-risk PE in a large real-world population.	61.2 ± 14.6	46	Percutaneous aspiration thrombectomy - FlowTriever System (Inari)	None	Composite of major adverse events (MAE)	MAE 1.8% mortality 0.3% at 48-hour follow-up and 0.8% at 30-day follow-up, with no device-related deaths.
2021	EXTRACT-PE ^{xxv} (Sista) (PEN)	Obser.	22	119	Acute intermediate-risk PE~ (symptomatic, normotensive, PE by CTA, RV/LV ratio >0.9)	59.8 ± 15	44.5	Percutaneous aspiration thrombectomy - Indigo Aspiration System (Penumbra)	None	Change in RV/LV ratio from baseline to 48hrs	0.43 (reduction of the RV/LV ratio at 48-hr); p < 0.0001. □ Major AEs [†] : 1.7% □ Major Bleeding: 1.7%
2019	FLARE ^{xxvi} (Tu) (INARI)	Obser.	18	116	Acute intermediate-risk PE (symptomatic, normotensive, PE by CTA, RV/LV ratio >0.9)	55.6 ± 13.7	46.2	Percutaneous aspiration thrombectomy - FlowTriever System (Inari)	None	Change in RV/LV ratio from baseline to 48hrs	0.38 (reduction of the RV/LV ratio at 48-hr); p < 0.0001. □ Major AEs: 3.8% □ Major Bleeding: 1.0%
2009	Meta-analysis ^{xxvii} (Kuo)	35 studies (6 Prosp, 29 Retro.)	Mult.	594	Acute high-risk PE	53	NR**	catheter-directed thrombolysis, and catheter embolectomy	None	Technical success: 86.5% Major procedural complication rate: 2.4% (see Analysis on subgroup reporting)	
2009	Rheolytic Thrombectomy ^{xxviii} (Chechi)	Obser., retrospective	1	51	Acute- and intermediate-risk PE	66.7 ± 13.8	51	AngioJet rheolytic thrombectomy	None	Mult, incl all-cause in-hosp mortality	Death in hospital: 15.7% □ Major bleeding: 17.8% □ Renal failure: 24%

1.4.2 Potential Benefits of the Vertex Pulmonary Embolectomy System Therapy

The Vertex Pulmonary Embolectomy System is intended to be used in patients with acute PE with diagnostic evidence of right ventricular dysfunction who are symptomatic but hemodynamically stable. The potential benefits of thrombectomy using the Vertex Pulmonary Embolectomy System include:

- Minimally invasive, lytic-free, single-session treatment

- Atraumatic access to the pulmonary arteries
- Enhanced intraprocedural control and navigation
- Efficient procedure completion

Minimally invasive, single-session, lytic-free treatment: Relative to surgical embolectomy, endovascular thrombectomy is a much less invasive procedure involving significantly less morbidity associated with access. The system allows for atraumatic access to the pulmonary arteries in order to aspirate thrombi. Compared to systemic or catheter-directed thrombolysis, thrombectomy using the Vertex Pulmonary Embolectomy System without lytics may reduce the systemic bleeding and intracranial hemorrhage risks associated with lytic-based treatments. Relative to catheter-directed thrombolysis, which requires two separate procedures to place and subsequently remove an infusion catheter with extensive patient monitoring in between, thrombectomy using the Vertex Pulmonary Embolectomy System carries the benefit of simplifying the treatment to one procedure for the patient while potentially reducing the resource burden associated with intensively monitoring the patient for an extended period.

Enhanced intraprocedural control and navigation: The Vertex Pulmonary Embolectomy System is designed to provide the procedural operator with a superior level of control while accessing the pulmonary arteries and thrombi. By creating a stable pathway into the pulmonary arteries that can be directed towards the vessels of interest, the Vertex Pulmonary Embolectomy System may reduce the likelihood of catheter prolapse into the right ventricle, as well as reducing inadvertent selection of non-target vessels. Additionally, this stabilization may provide a more precise and reliable means of accessing vessels that would be challenging to access with other catheter systems. SPIRARE I will gather various procedural data points related to vessel access, procedure time, ancillary device usage, and fluoroscopy and contrast utilization as surrogate markers to characterize this anticipated benefit.

Efficient procedure completion: A secondary benefit to enhanced intraprocedural control and navigation is the thorough reduction of clot burden and relieving right heart afterload, over an anticipated short procedure duration. To characterize the completeness of reducing both clot reduction and right heart afterload, SPIRARE I will gather secondary endpoint data on the Modified Miller Index reduction and various hemodynamic parameters as well as primary endpoint data on the RV/LV ratio reduction.

Use of the Vertex Catheter is anticipated to improve the efficiency of large-bore catheter aspiration for PE. Access to both the left and right pulmonary arteries is more feasible without having to exchange guidewires and losing access because the Vertex Catheter will maintain its fixed position. The ability to retain position within the pulmonary arteries may also reduce the total radiation exposure and contrast load for an equivalent procedure. SPIRARE I will collect data on radiation exposure and contrast utilization as comparative data.

Given that pulmonary embolism is a life-threatening disease with rapid progression to heart failure if not treated quickly, the ability to perform aspiration and quickly remove clots could be lifesaving. This treatment has the potential to benefit patients by reducing the hospital stay and need for intensive care. Beyond the potential benefits of the individual patient treated with the Vertex Pulmonary Embolectomy System, evaluating the safety, feasibility, and efficacy profile of pulmonary embolism treatment with the Vertex Pulmonary Embolectomy System can also contribute to the knowledge base of treatment options for PE patients using endovascular catheter-based approaches. Studies such as this can add important information to the collective knowledge on patient selection for the various catheter-directed aspiration thrombectomy techniques. Based on scientific literature, expert panels are publishing algorithms for the treatment of acute pulmonary embolism patients; this study evaluating Vertex Pulmonary Embolectomy System treatment could provide a significant refinement to those algorithms. Patients with acute PE who continue to be at risk of bleeding events despite the standard of care and optimal medical management may potentially benefit from this treatment. The potential benefits of pulmonary embolectomy treatment in this patient population are immediate relief from disabling symptoms of PE, recovery in heart rate, blood pressure, hemodynamics, and reduced right heart strain assessed by a change in RV/LV ratio.

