Event Severity	Mild	No limitation of usual activities, no therapy or only symptomatic therapy required to treat the injury or illness.
Event Severity	Moderate	Some limitation of usual activities or specific therapy is required.
Event Severity	Severe	Inability to carry out usual activities, hospitalization, emergency room treatment, life-threatening events, or death.
Injury	Cardiac Injury	Cardiac injury is defined as any damage to the heart requiring intervention to avoid permanent injury. Examples of possible cardiac injury : Acute heart failure • Acute myocardial infarction • Arrhythmia requiring intervention • Cardiac hematoma • Tricuspid or Pulmonic valve damage
Injury	Pulmonary Vascular Injury	
Pulmonary vascular injury is defined as perforation or injury of a major pulmonary arterial branch requiring intervention to avoid permanent injury.
 
Examples of possible pulmonary vascular injury: Arterial Venous Fistula • Dissection • Hemorrhage • Intimal flap • Perforation • Rupture • Thromboembolic occlusion resulting in permanent damage i.e. infarction

Study Population	Operative Screen Failure	Any eligible patient in whom the Vertex Catheter is not attempted or placed for any reason. Up until this point, the procedure may be converted to another therapeutic treatment or discontinued without the patient receiving any investigational treatment.
Study Population	Intent to Treat (ITT)	All patients who provide written informed consent, meet the inclusion/exclusion criteria, and in whom the Vertex Catheter is introduced past the pulmonic valve; enrollment occurs when Vertex catheter is introduced past the pulmonic valve. Any patient enrolled into the trial, but in whom the Vertex Pulmonary Embolectomy System is not able to access a pulmonary embolus is considered an Intent to Treat patient
Study Population	Screen Failure	Any screened patient who signs the ICF but does not meet the inclusion and exclusion criteria.

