2.6 Enrollment

Patients that fit the inclusion/exclusion criteria and provide written informed consent to participate in the study will be enrolled on intent to treat basis (ITT). An enrolled patient is defined as all patients who met the inclusion/exclusion criteria and who provide written informed consent, meet the inclusion/exclusion criteria, and in whom the Vertex Catheter is introduced past the pulmonic valve. The study will continue to enroll subjects until there are 10 (ten) enrolled and treated subjects.

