5.1.2 Operative Screen Failures

The following subjects are considered operative failures:

- Any eligible patient in whom the Vertex Catheter is not able to be introduced into the pulmonary artery for any reason.
- Until any point prior to the introduction of the Vertex Pulmonary Embolectomy System, the procedure may be converted to another therapeutic treatment or discontinued without the patient receiving any investigational treatment.

No further information will be collected on this patient; a study exit form (CRF) is required for all these patients. Any patient that experiences an adverse event after venous puncture but in whom the Vertex Catheter is not inserted will be monitored through discharge for safety and information about AEs will be collected in CRF, if applicable.

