9.2 Procedure (Day 0)

The following assessments will be conducted during the procedure:

1. Vital Signs
2. Venous puncture for Vertex-Pulmonary Embolectomy Procedure
3. Right heart catheterization (pre-and post-procedure) for ruling out pulmonary hypertension and Invasive hemodynamic assessment- systolic and mean PA pressures. Cardiac Output, Cardiac Index and Total Pulmonary Vascular Resistance will be assessed
4. Vertex Pulmonary Embolectomy System Procedure: For procedural details please refer to section **Section 4** above. NOTE: Hematocrit requirement (< 28%) must be confirmed prior to index procedure.
5. Following data will be collected:
 - Procedure time
 - Thrombectomy time
 - Number of Devices used in Pulmonary Arteries
 - Use of Adjunctive treatment
 - Number of times pulmonic Valve re-crossed with the same device
 - Use of stiff guidewire
 - Number of aspirations, location
 - Fluoroscopy time
 - Radiation dosage
 - Contrast volume
6. Device Accountability
7. Concomitant medications (Pre procedure)
8. Adverse Events/Device Deficiencies
9. Clinical Investigation Plan Deviations

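### The procedural data meant to show easier pulmonary artery access come only from patients in whom access succeeded, and no access rate over attempted patients is planned

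*Combined protocol and SAP*

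**What the plan says.** **Purpose of the data.** Section 1.4.2 lists atraumatic access and better control and navigation among the device's expected benefits. It says "SPIRARE I will gather various procedural data points related to vessel access, procedure time, ancillary device usage", along with fluoroscopy and contrast use, will serve as surrogate markers of the navigation benefit. It adds that "SPIRARE I will collect data on radiation exposure and contrast utilization as comparative data".

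**Who supplies them.** The Terms and Definitions table says "enrollment occurs when Vertex catheter is introduced past the pulmonic valve". Section 2.6 likewise limits enrolled patients to those "in whom the Vertex Catheter is introduced past the pulmonic valve", and adds: "The study will continue to enroll subjects until there are 10 (ten) enrolled and treated subjects".

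**What happens to the others.** Under section 5.1.2, an eligible patient whose catheter cannot be brought into the pulmonary artery, whatever the reason, is an operative screen failure. The rule is "No further information will be collected on this patient", apart from a study exit form and, where the catheter was not inserted, adverse events after venous puncture. Section 5.1.1 accepts that access failures may occur, through a guidewire that cannot be introduced or vessel spasm.

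**What is recorded elsewhere.** Section 2.2 gives every consenting subject a number and a log entry. Section 2.8 records the reason for each screen failure on the log and in the database. Section 13.1 includes procedural screen failures in the safety analysis but limits the efficacy analysis to the ITT and per-plan populations. It assigns no population to the procedural measures. The endpoints in sections 6.1 to 6.4 and the item 5 list in section 9.2 contain no access-success measure.

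**The concern.** Whether a new catheter can be brought into the pulmonary artery is a question that even ten patients can inform, and section 1.4.2 presents it as a benefit to be characterised. The enrolment rule makes success at that step a condition of entering the data set. Failures before the valve are replaced, so they do not appear in any planned procedural summary.

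Two things are at stake. First, a reader of the report could take entry in every enrolled patient as a performance result when it follows from the definition. Second, procedure time, fluoroscopy and contrast would be set beside other devices as comparative data without saying that failed attempts are left out. The second loss may be permanent: time, fluoroscopy and contrast not captured for a failed attempt may not be recoverable later.

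**Working it through.** The plan gives no access rate, sample-size calculation or power calculation, so there is no figure to reproduce. The check follows the rules through and then shows how large the effect could be.

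**Step 1: the denominator.** Enrolment requires passage of the pulmonic valve (Terms and Definitions; section 2.6). Failure to reach the pulmonary artery means no enrolment and no procedural data (section 5.1.2). Recruitment continues to ten enrolled and treated (section 2.6). With ten enrolled, pulmonary artery entry is 10/10 for any true access rate.

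**Step 2: the rate over all attempts.** Let f be the number of failed attempts (assumed). The rate is 10/(10 + f). The intervals are exact binomial 95% intervals for fixed n. They are approximate here because recruitment stops at the tenth success.

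| f (assumed) | Rate over attempts | 95% interval | Rate in enrolled set |
|---|---|---|---|
| 0 | 10/10 = 100% | 69.2 to 100% | 10/10 |
| 1 | 10/11 = 90.9% | 58.7 to 99.8% | 10/10 |
| 2 | 10/12 = 83.3% | 51.6 to 97.9% | 10/10 |
| 3 | 10/13 = 76.9% | 46.2 to 95.0% | 10/10 |
| 4 | 10/14 = 71.4% | 41.9 to 91.6% | 10/10 |

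**Step 3: how likely a failure is.** If the true access rate is p (assumed), the chance of at least one failure before the tenth success is 1 − p^10, and the expected number of failures is 10(1 − p)/p.

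- p = 0.95: 1 − 0.95^10 = 40%; 0.5 failures expected
- p = 0.90: 1 − 0.90^10 = 65%; 1.1 failures expected
- p = 0.80: 1 − 0.80^10 = 89%; 2.5 failures expected

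**Step 4: time, fluoroscopy and contrast.** Let k (assumed) be a failed attempt's value relative to the enrolled mean. The all-attempt mean divided by the enrolled mean is (10 + f·k)/(10 + f).

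| k (assumed) | f = 1 | f = 2 | f = 3 |
|---|---|---|---|
| 2.0 | 12/11 = 1.091 | 14/12 = 1.167 | 16/13 = 1.231 |
| 1.5 | 11.5/11 = 1.045 | 13/12 = 1.083 | 14.5/13 = 1.115 |
| 1.0 | 1.000 | 1.000 | 1.000 |
| 0.5 | 10.5/11 = 0.955 | 11/12 = 0.917 | 11.5/13 = 0.885 |

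Long failed attempts would make the enrolled mean look favourable; attempts abandoned early would do the reverse. The documents give nothing from which to choose k.

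**Step 5: the definitions behind the denominator.** The Terms and Definitions table describes an operative screen failure as a patient in whom the catheter was not attempted or placed. Section 5.1.2 describes one in whom it could not be brought into the pulmonary artery. The first mixes no attempt with a failed attempt; the second includes a catheter that was inserted but stopped short of the valve. A count of operative screen failures alone therefore does not identify failed attempts.

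**The case against.** The strongest reply is that failures are not hidden. Every consenting subject is numbered and logged, the reason for each screen failure goes into the database, and procedural screen failures enter the safety analysis. That stands: a count can probably be recovered. What is missing is a plan to report it as a rate, definitions that separate failed from unattempted introductions, and procedural data on the failures.

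A second reply is that access is wider than valve passage. A reader might infer that all access success is fixed at 100%. The documents do not support that. A patient whose embolus cannot be reached stays in ITT, and several benefits in section 1.4.2, such as holding position and reaching difficult branches, arise after the valve. The enrolled set can inform these, although no embolus-access rate is planned either.

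A reader might also infer that the procedural figures will look better than they should, or that the hardest anatomies are dropped. Step 4 shows that the direction can reverse, and section 5.1.2 covers failure for any reason, not anatomy alone.

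The item "Number of times pulmonic Valve re-crossed with the same device" might suggest that lost access followed by a device change goes unrecorded. Section 9.2 also counts devices used in the pulmonary arteries, so a change leaves a trace; only re-crossings by the replacement device are missed.

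Finally, the phrase "evaluating the safety, feasibility, and efficacy profile" in section 1.4.2 is background text about contributing to knowledge. Section 6 states the objective as safety and effectiveness, so the phrase does not amount to a promised feasibility endpoint.

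**Conclusion.** The point holds in limited form. The procedural data offered as evidence of easier access are conditional on the catheter passing the pulmonic valve. Entry into the pulmonary artery is 10/10 among ten enrolled patients by construction. One to four failures, an assumed range, would put the rate over attempts at 91% to 71%, with wide intervals.

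The effect on mean time, fluoroscopy and contrast has no known direction. With one to three failures it runs from 0.885 to 1.231 times the enrolled mean for k between 0.5 and 2, and it is nil if failed attempts resemble successful ones. If no attempt fails, nothing is lost.

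These are descriptive measures in a study for which section 13.2 plans no formal analysis. This point does not bear on either primary endpoint. It is an inexpensive improvement, worth making before enrolment starts because section 5.1.2 as written ends data collection on these patients.

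**What to change.** 1. **Section 5.1.2.** Record the section 9.2 item 5 data up to conversion or abandonment for every consented subject with venous puncture for the study procedure, and note whether introduction of the Vertex Catheter was attempted.
2. **Section 13.2.** Add as descriptive summaries, not new endpoints:
   - (a) pulmonary artery access: subjects with the catheter past the pulmonic valve, over all with venous puncture and also over all with Vertex introduction attempted, with reasons for failure. Both denominators are needed: the first keeps the section 5.1.1 access failures that occur after puncture, while the second leaves out patients stopped for reasons unrelated to the catheter, such as the pulmonary artery pressure exclusion found at right heart catheterization;
   - (b) embolus access: subjects in whom an embolus was reached, over all enrolled;
   - (c) procedure time, fluoroscopy time and contrast volume for all attempts, beside the enrolled set.
3. **Definitions.** Reconcile the operative screen failure wording in Terms and Definitions with section 5.1.2.
4. **Optional.** Count pulmonic valve re-crossings with any device.

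The cost is one CRF page per failed attempt and a few table rows. The downside for the sponsor is a possibly less favourable performance figure. Treatment and enrolment rules stay as they are.
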